5.0 METHODOLOGY

5.1 Entry Criteria

5.1.1 Diagnosis/Condition for Entry into the Trial

Patients with early stage (T1bN0 and T2aN0) peripherally located lesions that are cytologically or histologically proven and eligible for surgical resection. Although varying definitions for centrally located tumors have been used, the International Association for the Study of Lung Cancer has recommended the following: a tumor within 2 cm in all directions of any mediastinal critical structure, including the bronchial tree, esophagus, heart, brachial plexus, major vessels, spinal cord, phrenic nerve, and recurrent laryngeal nerve (58).

5.1.2 Subject Inclusion Criteria

In order to be eligible for participation in this trial, the subject must:

1. Have a histologically or cytologically confirmed diagnosis of early stage (T1bN0 and T2aN0) peripherally located NCSLC, eligible for surgical resection.
2. Be willing and able to provide written informed consent/assent for the trial.
3. Be ≥ 18 years of age on day of signing informed consent.
4. Have measurable disease based on RECIST 1.1.

5. Must provide tissue from a core or excisional biopsy of the primary tumor lesion.
6. Have a performance status of 0-1 on the ECOG Performance Scale.
7. Demonstrate adequate organ function as defined in Table 1, all screening labs should be performed within 10 days of treatment initiation.

Table 1. Adequate Organ Function Laboratory Values

System	Laboratory Value
Hematological	
Absolute neutrophil count (ANC)	≥1,500 /mcL
Platelets	≥100,000 / mcL
Hemoglobin	≥9 g/dL or ≥5.6 mmol/L
Renal	
Serum creatinine OR Measured or calculated creatinine clearance (GFR can also be used in place of creatinine or CrCl)	≤1.5 X upper limit of normal (ULN) OR ≥45 mL/min for subject with creatinine levels > 1.5 X institutional ULN
Hepatic	
Serum total bilirubin	≤ 1.5 X ULN OR Direct bilirubin ≤ ULN for subjects with total bilirubin levels > 1.5 ULN
AST (SGOT) and ALT (SGPT)	≤ 2.5 X ULN OR ≤ 5 X ULN for subjects with liver metastases

8. Female subject of childbearing potential should have a negative urine or serum pregnancy within 72 hours prior to receiving the first dose of study medication. If the urine test is positive or cannot be confirmed as negative, a serum pregnancy test will be required.
9. Female subjects of childbearing potential should be willing to use 2 methods of birth control or be surgically sterile, or abstain from heterosexual activity for the course of the study through 120 days after the last dose of study medication. Subjects of childbearing potential are those who have not been surgically sterilized or have not been free from menses for > 1 year.
10. Male subjects should agree to use an adequate method of contraception starting with the first dose of study therapy through 120 days after the last dose of study therapy.

5.1.3 Subject Exclusion Criteria

The subject must be excluded from participating in the trial if the subject:

1. Is currently participating in or has participated in a study of an investigational agent or using an investigational device within 4 weeks of the first dose of treatment.
2. Has a diagnosis of immunodeficiency or is receiving systemic steroid therapy or any other form of immunosuppressive therapy within 7 days prior to the first dose of trial treatment.
3. Has had a prior monoclonal antibody within 4 weeks prior to study Day 1 or who has not recovered (i.e., ≤ Grade 1 or at baseline) from adverse events due to agents administered more than 4 weeks earlier.

4. Has had prior chemotherapy, targeted small molecule therapy, or radiation therapy within 2 weeks prior to study Day 1 or who has not recovered (i.e., \leq Grade 1 or at baseline) from adverse events due to a previously administered agent.
 - Note: Subjects with \leq Grade 2 neuropathy are an exception to this criterion and may qualify for the study.
 - Note: If subject received major surgery, they must have recovered adequately from the toxicity and/or complications from the intervention prior to starting therapy.
5. Has a known additional malignancy that is progressing or requires active treatment. Exceptions include basal cell carcinoma of the skin, squamous cell carcinoma of the skin, or in situ cervical cancer that has undergone potentially curative therapy.
6. Has an active autoimmune disease requiring systemic treatment within the past 3 months or a documented history of clinically severe autoimmune disease, or a syndrome that requires systemic steroids or immunosuppressive agents. Subjects with vitiligo or resolved childhood asthma/atopy would be an exception to this rule. Subjects that require intermittent use of bronchodilators or local steroid injections would not be excluded from the study. Subjects with hypothyroidism stable on hormone replacement or Sjorgen's syndrome will not be excluded from the study.
7. Has a history of (non-infectious) pneumonitis that required steroids, evidence of interstitial lung disease or active, non-infectious pneumonitis.
8. Has an active infection requiring systemic therapy.
9. Has a history or current evidence of any condition, therapy, or laboratory abnormality that might confound the results of the trial, interfere with the subject's participation for the full duration of the trial, or is not in the best interest of the subject to participate, in the opinion of the treating investigator.
10. Has known psychiatric or substance abuse disorders that would interfere with cooperation with the requirements of the trial.
11. Is pregnant or breastfeeding, or expecting to conceive or father children within the projected duration of the trial, starting with the pre-screening or screening visit through 120 days after the last dose of trial treatment.
12. Has received prior therapy with an anti-PD-1, anti-PD-L1, anti-PD-L2, anti-CD137, or anti-Cytotoxic T-lymphocyte-associated antigen-4 (CTLA-4) antibody (including ipilimumab or any other antibody or drug specifically targeting T-cell co-stimulation or checkpoint pathways).
13. Has a known history of Human Immunodeficiency Virus (HIV) (HIV 1/2 antibodies).
14. Has known active Hepatitis B (e.g., HBsAg reactive) or Hepatitis C (e.g., HCV RNA [qualitative] is detected).
15. Has received a live vaccine within 30 days prior to the first dose of trial treatment.

5.2 Sample size

Twenty patients will be included in this study. A formal power analysis to calculate a sample size is not feasible due to the explorative nature of this trial. The sample size of 10 patients in each arm is based on two previous analyses that we performed. In a cohort of 9 head and neck cancer patients we were able to find significant differences in the expression of activation markers between different dendritic cell subsets (data on file). In a cohort of 9

melanoma patients we were able to find significant differences in the expression of activation markers between dendritic cell subsets of patients with a Breslow thickness more or less than 1.5 mm (60).

5.3 Pretreatment imaging

5.3.1 Prestudy diagnostic and staging imaging

Standard of care pre-treatment staging includes a diagnostic CT chest and a whole-body static PET-CT.

5.3.2 ⁸⁹Zr-pembrolizumab PET

5.3.2.1 Radiolabeling of pembrolizumab and quality controls

Using standard procedures for the production of ⁸⁹Zr-labeled monoclonal antibodies, several clinical ⁸⁹Zr-immuno-PET studies have been performed, are ongoing, or will be started shortly. In these ongoing studies safety was confirmed. ⁸⁹Zr is coupled to pembrolizumab via the bifunctional chelator desferal. ⁸⁹Zr will be produced at the VU University Medical Center by Cyclotron BV according to procedures essentially as described before (51). Radiochemical purity of the purified ⁸⁹Zr used for labeling will be according to the specification as described in the same paper. ⁸⁹Zr-mAb conjugates produced in this way were found to be fully stable in vitro and in vivo as shown in several preclinical and clinical studies (61). Using the same procedures, the following conjugates have been produced and administered to patients without any adverse event: ⁸⁹Zr-cMAb U36, ⁸⁹Zr-ibritumomab tiuxetan (ZevalinTM), ⁸⁹Zr-rituximab (RituxanTM), ⁸⁹Zr-trastuzumab (HerceptinTM), ⁸⁹Zr-bevacizumab (AvastinTM) and ⁸⁹Zr-cetuximab (ErbixTM) (56, 62).

Radiolabeling of pembrolizumab with ⁸⁹Zr will be performed according to Standard Operating Procedures (SOPs) within the premises of the Radionuclide Center (RNC) of the Department of Nuclear Medicine & PET research. The whole process will be performed according to state-of-the-art Good Manufacturing Practice (GMP) standards. This production site was recently inspected by the Dutch Health Care Inspectorate and is licensed to manufacture tracers for human use according to the latest EU guidelines. This site has also been audited by the largest EU pharma-companies.

The procedures for radiolabeling of mAbs with ⁸⁹Zr have been validated with respect to the synthesis procedure and the final quality of the prepared conjugates. The radiochemical purity, immunoreactivity and endotoxin content of every batch will be assessed prior to administration to a patient. The radiochemical purity as assessed by ITLC (instant thin layer chromatography) and HPLC (high performance liquid chromatography) should always be >90%, preferably >95%, while the immunoreactive fraction as assessed by cell binding assay, should always exceed 70%. This analysis will be performed according to a procedure essentially as described by Lindmo et al (63). The endotoxin content is determined according to pharmacopeia using an endosafe PTS reader. Sterility of each ⁸⁹Zr-pembrolizumab batch will be assured by performing a media fill immediately after final sterilization of each batch. The expiration time of the conjugates will be defined in validations.

5.3.2.2 Radiation exposure

For the patient the radiation dose of administering 37 MBq of ^{89}Zr -pembrolizumab is expected to be around 18 mSv. Low dose CT scans used for attenuation correction will give an additional dose of 3 mSv per CT. The effective dose is therefore expected to be around 24 mSv for the immune-PET scan. After injection no shielding is required and the patient can immediately go home with instructions.

5.3.2.3 Injection procedure

The injection will take place at the department of Nuclear Medicine & PET research. A tracer dose (2 mg) of ^{89}Zr -pembrolizumab will be injected as a bolus of 20 mL with flushing (10 mL physiologic saline).

During administration of ^{89}Zr -pembrolizumab the patient will be monitored closely and appropriate measurements will be performed whenever judged necessary. In case of an allergic reaction to ^{89}Zr -pembrolizumab the patient will be treated according to the standard clinical protocol. In this situation, the patient will be eliminated from the study.

5.3.2.4 Blood sample analysis

Blood samples (7 mL) will be withdrawn at 10 min post-injection, 72 hours and 144 hours post-injection of ^{89}Zr -pembrolizumab to determine ^{89}Zr -kinetics based on measurements of radioactivity.

5.3.2.5 ^{89}Zr -pembrolizumab PET procedure

All PET scans will be performed on a Philips Ingenuity TF PET/CT scanner.

All patients will undergo two whole body PET scans at $t = 72$ and $t = 144$ hours post-injection. The PET scans will be preceded by a 30 mAs low-dose CT, used for attenuation correction and anatomical localization of the PET-signal. Following CT, a total body PET scan will be acquired. PET scans consist of 10-12 bed positions, depending on the length of the patient, of 5 minutes each. Total acquisition time per scan, including low dose CT will be around 60 minutes.

PET data will be normalized and corrected for randoms, tissue attenuation, decay, scatter and dead time. PET-CT data will be reconstructed with TF-OSEM, resulting in a transaxial spatial resolution of ~ 7 mm in the centre of the field of view. Regions of interest (ROIs) will be defined using the CT images which are co-registered to the PET-CT data. ROIs around the organs which accumulate ^{89}Zr (e.g. liver, lung and other metastatic lesions) will be drawn manually directly on the PET images. All tissue concentrations will be related to the blood concentration (venous samples). The radioactivity concentrations in all regions for all imaging time points will be recorded digitally in a spread sheet.

Quantitative accuracy of ^{89}Zr -PET scans was previously confirmed in our center using phantom studies and comparisons between PET-derived and biopsy tumor radioactivity concentrations (64, 65).

5.3.2.6 Analysis of PET data

Tumor volumes of interest will be delineated using semi-automated in-house developed software. SUV_{max} , SUV_{mean} and SUV_{peak} will be calculated for the tumor and visible lymph nodes (67-69).

5.4 On-treatment imaging

The diagnostic CT chest will be repeated within two weeks before surgical resection.

5.4.1 Quantitative changes in lung density

The aim of these measurements is to determine whether a relationship exists between SBRT dose and radiographic lung injury, as measured by CT density changes (70).

Contours of selected isodose levels (0.5 Gy, 3 Gy, 6 Gy, 12 Gy, 18 Gy, 24 Gy, 36 Gy, and 50 Gy) will be exported from the planning system along with the contours of the lung and internal target volume, and the average-intensity CT dataset. These isodose lines are chosen to provide a wide range of doses and large enough volumes between lines to allow for meaningful density measurements. This results in a total of eight evaluable dose-density regions in the ipsilateral lung. In the contralateral lung, only one dose-density region (receiving ≥ 3 Gy) will be analyzed, because it is uncommon for the contralateral lung to receive >5 Gy. The contralateral lung receiving <3 Gy will be considered unirradiated and as such used to correct for baseline differences between scanners. The regions receiving >50 Gy are not analyzed because these volumes are small and because small errors in registration can place a few millimeters of regressing or stable tumor within that volume, artificially increasing density measurements. After deformation of the follow-up scans, isodoses from the endinspiratory phase of the planning CT scan will then be overlaid on the deformed follow-up scan, and changes in Hounsfield unit (HU) density assessed.

The air-filled fraction (f_{air}) will be calculated from HU density using the formula $f_{\text{air}} = \frac{HU - NCT}{-1000 - NCT}$, where NCT is the CT number in HU (71). f_{air} represents the percentage of lung tissue that contains air, and it decreases with increasing CT density.

5.5 Ultrasound endoscopy guided cytological lymph node aspiration for immunological cell composition (EBUS FACS)

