8.4 Analysis of CT data

The pre- and post SBRT +/- pembrolizumab CT scans will be assessed for HU density and f_{air} values as outlined in section 5.4.1. Baseline and post induction treatment values within patients will be assessed by the paired t-test. Comparison of the baseline and posttreatment values between the radiotherapy and radiotherapy + pembrolizumab arms will be assessed per time-point by the independent samples t-test.

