10.3.5 Safety of the trimodality approach

Combining SBRT with surgery appears safe. At least 4 small studies have reported on patients who have undergone surgery for salvage in patients who have recurred after SBRT (42-45). Since the results of SBRT seem to be equivalent to those of surgery we believe that the delay to surgical resection is not harmful and might even be beneficial for patients. The addition of pembrolizumab to SBRT might lead to a higher rate of pneumonitis. However, the incidence of pneumonitis depends on the target volume and is rarely seen with treatment of early stage lung cancer. Because only patients with peripheral tumors are eligible for this trial and patients receive a lobectomy according to national guidelines on the treatment for NSCLC, the irradiated lung lobe will be resected and resection margins (i.e. central bronchial and vascular structures) are not involved in the radiation target volume.

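### The contralateral-lung correction removes any pembrolizumab effect on CT density that both lungs share from the between-arm comparison, and no uncorrected or contralateral-by-arm result is planned

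*Combined protocol and SAP*

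**What the plan says.** Section 5.4.1 gives the purpose of the measure: "The aim of these measurements is to determine whether a relationship exists between SBRT dose and radiographic lung injury, as measured by CT density changes". Density change is assessed in regions bounded by isodose lines, and one lung region serves as the reference: "The contralateral lung receiving <3 Gy will be considered unirradiated and as such used to correct for baseline differences between scanners". The section does not say whether this correction is a subtraction or a scaling, or which scans it is applied to.

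Section 8.4 takes the HU density and air-filled fraction (f_air) from 5.4.1 and uses them for a second purpose: "Comparison of the baseline and posttreatment values between the radiotherapy and radiotherapy + pembrolizumab arms will be assessed per time-point", by independent-samples t-test. No uncorrected analysis and no contralateral under-3-Gy result by arm is listed.

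Section 10.3.5 accepts that the drug may act on lung: "The addition of pembrolizumab to SBRT might lead to a higher rate of pneumonitis". Section 4.1.7 cites pneumonitis in 1.8% of pembrolizumab-treated patients in a phase I trial.

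For f_air, section 5.4.1 says that it "will be calculated from HU density using the formula" (HU − NCT)/(−1000 − NCT), "where NCT is the CT number in HU (71"). It adds that f_air falls as CT density rises.

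**The concern.** Contralateral lung under 3 Gy is close to unirradiated, but in one arm it is not untreated. Pembrolizumab is systemic, so a reference region inside the lung carries whatever diffuse drug effect reaches that lung. Aligning a follow-up scan on that region removes the effect from the corrected values, in the combination arm only.

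For the within-patient dose-injury question this does little harm. For the arm comparison in 8.4 it matters, because that is the only between-arm comparison of lung imaging in section 8. The ⁸⁹Zr-pembrolizumab PET is done before treatment and in one arm. The histology of surrounding lung (7.1.2.7.2, 8.2.1) is a 0-to-3 score confined to the resected lobe. The safety rule in 8.1 counts only pneumonitis of grade 3 or higher. A null CT comparison could therefore be read as evidence that pembrolizumab adds no density change, when part of such a change was removed by construction.

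**Working it through.** **1. The plan's own count.** The listed lines are: "Contours of selected isodose levels (0.5 Gy, 3 Gy, 6 Gy, 12 Gy, 18 Gy, 24 Gy, 36 Gy, and 50 Gy"). Leaving out lung above 50 Gy, the bands are 0–0.5, 0.5–3, 3–6, 6–12, 12–18, 18–24, 24–36 and 36–50 Gy, which makes eight. This matches "This results in a total of eight evaluable dose-density regions in the ipsilateral lung", provided lung below 0.5 Gy is counted; strictly between lines there are seven. Nothing below depends on this. The plan states no effect size, SD or power for the CT analysis.

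**2. Is the follow-up reference lung drug-exposed?**
- Pembrolizumab starts on the first day of radiotherapy and is planned for two three-weekly cycles (5.6.2). The second dose falls at about day 21 (7.1.2.10).
- The flow chart puts surgery at days 56 to 70. The repeat CT falls within the two weeks before surgery (5.4), so no earlier than day 56 − 14 = 42.
- The follow-up CT therefore comes about three weeks or more after the second scheduled dose. The baseline scan precedes therapeutic pembrolizumab, and the SBRT-only arm never receives it.

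**3. What the correction removes.** Assume an additive model and a subtractive correction. Let T = 1 in the combination arm and 0 otherwise, and let:
- s = scanner and inspiration shift
- r(d) = radiation effect at dose d
- p = diffuse drug effect in the measured region
- k = share of p also present in the contralateral reference (0 to 1)
- i(d) = drug enhancement of radiation injury at dose d

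Then:
- change in region = s + r(d) + T·[p + i(d)]
- change in reference = s + T·k·p
- corrected change = r(d) + T·[(1 − k)·p + i(d)]

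The expected between-arm difference is (1 − k)·p + i(d) after correction and p + i(d) without it. If 8.4 compares follow-up levels rather than changes, the expression is the same in expectation, because randomization balances baseline.

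All HU values in this table are assumptions:

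| p | i(d) | true difference | corrected, k = 0 | k = 0.5 | k = 1 |
|---|---|---|---|---|---|
| 20 | 0 | 20 | 20 | 10 | 0 |
| 20 | 30 | 50 | 50 | 40 | 30 |
| 50 | 0 | 50 | 50 | 25 | 0 |
| 50 | 30 | 80 | 80 | 55 | 30 |

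For p > 0 and k > 0 the loss is always towards no difference, and i(d) is never lost. With NCT fixed, f_air is linear in HU, so the loss carries over: with a reference of 0 HU, 20 HU removed is 20/1000 = 0.02 in f_air.

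**4. Illustrative power.** With 10 per arm (5.2), two-sided 0.05, exact t-test, i(d) = 0 and a true effect of 1 SD, power is 0.56 if nothing cancels, 0.185 if half cancels and 0.05 if all cancels. This holds the SD constant; uncorrected values would in practice be noisier.

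**5. The f_air formula.**
- HU and NCT both the measured CT number, as the definition reads: 0 at every value, and 0/0 at −1000 HU.
- NCT measured and HU a fixed 0 or +50: at −700 HU, 700/(−300) = −2.33 or 750/(−300) = −2.5, impossible for a fraction.
- HU measured and NCT a fixed 0 or +50: at −700 HU, (−700)/(−1000) = 0.70 or (−750)/(−1050) = 0.714. This is sensible and falls as density rises.

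Only the third reading works, and it is not the one that the text defines.

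**The case against.** The strongest reply is that the measure is being judged against an aim it does not have. Section 5.4.1 asks about SBRT dose, section 3.3 speaks of radiation-induced change, and lung under 3 Gy is a sound reference for both. That stands for the within-patient analysis. It does not cover the arm comparison, which 8.4 adds on the same values.

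A reader might infer that any pembrolizumab effect on lung cancels. The documents do not support this. Only the shared part cancels, and completely only if the effect is uniform and the correction subtractive, which 5.4.1 does not state. Enhancement of radiation injury, the drug effect closest to the section's aim, is kept. Nor does the text say that each scan is corrected.

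The evidence for a diffuse effect is also thin. Section 10.3.5 goes on to tie pneumonitis to target volume, which points to local injury. At 1.8%, ten combination patients would yield 10 × 0.018 = 0.18 expected cases and a chance of 1 − 0.982^10 ≈ 17% of seeing any. That rate does not measure subclinical density change, but the documents give no figure for such change either.

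A reader might likewise conclude that f_air is zero everywhere and worthless. That depends on equating HU with NCT, while the following sentence shows that a varying measure is meant. A typesetting or text-conversion error in the equation cannot be excluded. It is one mis-defined symbol.

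Finally, replacing the lung reference with air and soft tissue would not be a clear improvement, since those references do not correct for inspiration level.

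**Conclusion.** The concern holds in a limited form. The correction suits the dose-injury aim. In the between-arm comparison of 8.4 it removes k·p, the part of a pembrolizumab effect that contralateral lung shares, and so biases that comparison towards no added lung injury. The loss runs from nothing (k = 0) to the whole diffuse effect (k = 1); dose-dependent enhancement is retained throughout. This assumes a subtractive correction that uses the follow-up scan's contralateral lung, which is what aligning scanners between baseline and follow-up would require but which the plan leaves unstated. The size of any diffuse effect is unknown, and every HU value above is an assumption.

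The consequence is confined to an exploratory analysis with no decision rule. It is still worth correcting, because the direction of the bias is known and the results needed to reveal it are not planned. The f_air point is a secondary correction of wording.

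**What to change.** In 5.4.1 and 8.4:

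- State how the contralateral correction is computed (subtraction or scaling) and to which scans it applies.
- Report the change in contralateral lung under 3 Gy by arm as an outcome in its own right.
- Give the ipsilateral between-arm result both with and without the correction. Under a subtractive correction, the uncorrected difference equals the corrected difference plus the contralateral difference (for p = 20, i = 30, k = 0.5: 40 + 10 = 50), so the amount removed is visible.
- Define HU as the measured regional mean and NCT as a stated fixed value for airless tissue, checked against the cited source.

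The cost is wording and a few more t-tests; the lung and 3 Gy contours are already exported, so no new scans are needed. The downside is that uncorrected and contralateral values carry scanner and inspiration noise, which with 10 per arm will widen their intervals. A non-lung scanner reference, such as tracheal air with a fixed soft-tissue region, could be an optional sensitivity analysis at the price of two small regions per scan. It should not replace the lung reference, because it does not correct for inspiration level.
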